3.0 INVESTIGATIONAL PLAN

3.1 Study Design and Patient Follow-up

This is a prospective, non-randomized, multicenter, pivotal IDE study evaluating the Investigational Devices with the ST Monitoring Feature. The Analyze ST study is designed to demonstrate the safety and efficacy of the ST Monitoring Feature in the Investigational Devices. The sensitivity of the ST Monitoring Feature for detecting acute coronary syndrome events will be the primary efficacy endpoint. The primary safety endpoint will be assessed by reporting the percentage of patients who experience a false positive detection during the 12 months following a 3 month run-in period.

The goal of the 3 month run-in period is to:

1. Identify patients whose EGM rhythm or morphology is unsuitable for chronic ST monitoring
2. Provide data collection for review in order to adjust or optimize ST feature parameters

[figure not shown]
Data collection for the purposes of the FDA market approval application will be considered to be complete when the primary safety endpoint data are available and at least 41 clinical events have occurred. It is estimated that up to 5,228 patients at

Statistical Analysis Plan

approximately 200 centers will be enrolled in the study with a follow up of 12 months to meet the primary study endpoints.

A flow diagram of the study design is below.

Study Flow Diagram

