4.3 Analysis of Safety

4.3.1 Preliminary Safety Assessment Phase

An initial assessment of the proportion of patients free from complications due to unnecessary procedures resulting from false positive events will be conducted on the first 500 patients to complete 6 months of follow-up. In patients with an upgraded Fortify[®] ST device, the 6 months of follow-up begins with either their Baseline visit or the Baseline Upgrade visit (during which the firmware upgrade occurs). In patients with Fortify Assura ST[®] and Ellipse ST[®], the 6 months of follow-up begins with the Baseline visit. For those patients with Fortify Assura ST[®] and Ellipse ST[®], the survival time for patients who experience a complication will be calculated as the number of days from the Baseline visit (when the Patient Notifier is activated) to the date of the procedure-related complication. For those patients with Fortify[®] ST devices, the survival time will be calculated as the number of days from either the Baseline visit or the Baseline Upgrade visit (i.e., whichever visit the patient received the firmware upgrade) to the date of the procedure-related complication is first discovered. For patients who withdraw without experiencing a complication prior to analysis, their survival time will be censored at the date of withdrawal. For patients who have not experienced complications at the time of analysis, their survival time will be censored on the date of the analysis.

All patients who have the Patient Notifier turned ON at the Baseline visit or the Baseline Upgrade visit and have completed their 6-month follow up visit or 6 months of follow up since being upgraded will be included in this analysis.

Statistical Analysis Plan

Complications related to unnecessary procedures resulting from false positive events are defined as any procedure-related or test-related complications that occur in a patient in which a Type I ST episode is classified as a false positive according to the criteria described in section 3.2.3. All clinical events will be adjudicated by an independent and blinded Clinical Event Committee for the purposes of determining whether the event was related to ischemia or acute coronary syndrome and whether it was procedure or test related. Complications related to procedures or tests may include, but are not limited to:

- Air embolism
- Allergic reaction to contrast media
- AV fistula
- Bleeding
- Cardiac tamponade
- Contrast nephropathy

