- Formation of hematomas or cysts
- Infection
- Myocardial infarction
- Peripheral nerve injury
- Pneumothorax
- Pseudo-aneurysm
- Stent thrombosis
- Stroke
- Thromboemboli
- Venous occlusion
- Venous or cardiac perforation

Analysis

- A Kaplan-Meier estimate of the proportion of patients free from complications arising from a false positive event through the 6 month follow-up visit will be provided with a 95% lower bound on the estimate using Greenwood's formula for the variance of the Kaplan-Meier estimator. If no events have been observed, then a Clopper-Pearson 95% exact lower confidence bound for the proportion of patients free from complications due to unnecessary procedures resulting from false positive events will be provided.
- A tabular presentation of ER visits, doctor office visits, or any medical care will be presented, stratified by false positive, true positive and false negative events.
- The proportion of patients with false positive events, with the count of false positive, true positive and false negative events will be provided. A preliminary estimate of sensitivity will be calculated.
- The proportion of patients with the ST monitoring feature turned off after the Programming and Baseline visits will be tabulated along with the reason for the turning off the ST monitoring feature.
- Baseline demographics and site enrollment will be tabulated.

Statistical Analysis Plan

The above analyses will be presented overall and by the following subgroups:

- Coronary artery disease patients with cardiomyopathy
- Coronary artery disease patients without cardiomyopathy
- Patients with abnormal baseline ECGs, for each of six abnormal subgroup categories
- Patients with normal baseline ECGs
- Patients with arrhythmias
- Gender
- Patients alerted via Merlin.net and patients alerted via device Patient Notifier

Additional Analysis

An analysis will be performed that includes all clinical events using a GEE logit-link linear model to estimate the sensitivity with a working correlation that provides a robust estimator of the variance adjusting for multiple clinical events within patients.

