An empirical analysis will be provided for the sensitivity of the ST Monitoring Feature to detect clinical events using the estimator described in the Primary Analysis section. The standard error of this empirical estimate will be calculated as the standard deviation of a bootstrap distribution. The bootstrap distribution will be constructed using 1,000 bootstrap resamples. Each bootstrap resample will be performed at the patient level (in order to preserve the correlation structure of multiple events within one patient, if the occurs), and each resample will have a total sample size equal to the total number of evaluable patients. A two-sided 95% bootstrap confidence interval will be provided.

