4.4 Analysis of Efficacy

4.4.1 Primary Efficacy Endpoint

The efficacy endpoint will be evaluated as the sensitivity of the ST Monitoring Feature to detect clinical events. Sensitivity of the ST Monitoring Feature to detect clinical events will be calculated as the number of True Positive events (as defined in section 3.2.3) divided by the total number of ACS clinical events.

$$\text{Sensitivity} = \frac{\text{\# of TP events}}{\text{Total number of ACS events}}$$

A clinical event is considered to be related to the onset of a Type I ST episode if the clinical event occurs within 72 hours after the onset of a Type I ST episode.

The hypothesis is formally expressed as follows:

H_0 : Sensitivity \leq 50%

H_a : Sensitivity $>$ 50%

The desired outcome is to demonstrate that the sensitivity of the ST Monitoring Feature is greater than 50%. The null hypothesis will be rejected at the 2.5% significance level if the lower bound of the 95% confidence interval for sensitivity is greater than 50%. The lower confidence bound will be calculated using the Wilson score interval method.

Patient Group

All enrolled patients who have a successful implant or system revision, complete the Baseline follow up visit and have the ST Monitoring Feature and Patient Notifier turned ON, and experience clinical events will be included in the evaluation of this study endpoint. Data collection towards the study endpoint will begin after the Baseline visit.

Further, the analysis population for the primary efficacy endpoint will be those subjects with the Fortify[®] ST (upgraded), Fortify Assura[®] ST and Ellipse[®] ST devices. The data from subjects with a Fortify[®] ST prior to being upgraded will not be included in this analysis.

Statistical Analysis Plan

Analysis

Primary Analysis

The expected sensitivity for ST Monitoring Feature will be estimated by the number of true positive events divided by the total number of ACS events.

The 95% confidence limits will be calculated for sensitivity using the Wilson score interval method⁷ for a binomial proportion. The null hypothesis will be rejected if the lower bound of the 95% confidence limit is greater than 50%.

Additional Analysis

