4.5 Overall sample size and data cut-off

[figure not shown]
The total number of patients required for enrollment in order to satisfy the primary endpoints and the secondary endpoint is driven by the sample size requirement to satisfy the primary efficacy endpoint. Thus the total sample size required for this study is 5,228.

Data collection for the purposes of the FDA market approval application will be considered to be complete when the primary safety endpoint data are available and at least 41 clinical events have occurred.

Following submission of the clinical data, patients will continue to be followed until closure of the study for providing long-term follow up on the Investigational Devices.

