- Formation of hematomas or cysts
- Infection
- Myocardial infarction
- Peripheral nerve injury
- Pneumothorax
- Pseudo-aneurysm
- Stent thrombosis
- Stroke
- Thromboemboli
- Venous occlusion
- Venous or cardiac perforation

Analysis

- A Kaplan-Meier estimate of the proportion of patients free from complications arising from a false positive event through the 6 month follow-up visit will be provided with a 95% lower bound on the estimate using Greenwood's formula for the variance of the Kaplan-Meier estimator. If no events have been observed, then a Clopper-Pearson 95% exact lower confidence bound for the proportion of patients free from complications due to unnecessary procedures resulting from false positive events will be provided.
- A tabular presentation of ER visits, doctor office visits, or any medical care will be presented, stratified by false positive, true positive and false negative events.
- The proportion of patients with false positive events, with the count of false positive, true positive and false negative events will be provided. A preliminary estimate of sensitivity will be calculated.
- The proportion of patients with the ST monitoring feature turned off after the Programming and Baseline visits will be tabulated along with the reason for the turning off the ST monitoring feature.
- Baseline demographics and site enrollment will be tabulated.

Statistical Analysis Plan

The above analyses will be presented overall and by the following subgroups:

- Coronary artery disease patients with cardiomyopathy
- Coronary artery disease patients without cardiomyopathy
- Patients with abnormal baseline ECGs, for each of six abnormal subgroup categories
- Patients with normal baseline ECGs
- Patients with arrhythmias
- Gender
- Patients alerted via Merlin.net and patients alerted via device Patient Notifier

Additional Analysis

An analysis will be performed that includes all clinical events using a GEE logit-link linear model to estimate the sensitivity with a working correlation that provides a robust estimator of the variance adjusting for multiple clinical events within patients.

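### The 500-patient preliminary assessment puts a logit GEE and a bootstrap interval on sensitivity, but the plan's own figures imply only about two ACS events in the minimum follow-up

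*Protocol*

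**What the plan says.** The preliminary safety assessment is "conducted on the first 500 patients to complete 6 months of follow-up" (Protocol 4.3.1; the SAP has the same text). Its main quantity is freedom from complications of unnecessary procedures. The same section also covers sensitivity, in four places:

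- It requires counts of false positive, true positive (TP) and false negative (FN) events, and adds: "A preliminary estimate of sensitivity will be calculated" (SAP 4.3.1).
- These analyses are to be repeated by subgroup, including each of six ECG abnormality categories.
- Under Additional Analysis it adds a model "using a GEE logit-link linear model to estimate the sensitivity with a working correlation that provides a robust estimator of the variance", to allow for several events in one patient.
- It then adds a bootstrap by patient, with 1,000 resamples the size of the evaluable cohort: "The standard error of this empirical estimate will be calculated as the standard deviation of a bootstrap distribution". A two-sided 95% interval is to be given.

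For the whole study, Protocol 3.1 states that up to 5,228 patients at "approximately 200 centers will be enrolled in the study with a follow up of 12 months to meet the primary study endpoints". Protocol 4.5 says: "Thus the total sample size required for this study is 5,228". Data collection for the market application is complete when the "primary safety endpoint data are available and at least 41 clinical events have occurred".

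The final sensitivity test in 4.4.1 uses a Wilson interval, with a bootstrap as an additional analysis. The GEE does not appear there.

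**The concern.** A robust variance and a patient-level bootstrap both need a reasonable number of patients with an ACS event. The 500-patient phase is a small part of a study that is sized to yield 41 events. If only a few ACS events fall in it, they may well be all detected or all missed. Every bootstrap resample that contains an event then returns the same value, so the standard error is zero, and the logit of 0% or 100% is infinite.

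Section 4.3.1 has an exact fallback for sparse data on complication freedom but none for sensitivity. It also has no rule for resamples that contain no ACS event. The report goes to the FDA and the DSMB (section 4.2), so it could show them a sensitivity of 100% with no apparent uncertainty, based on two events.

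**Working it through.** **Inputs from the documents.** 41 events, 5,228 enrolled patients and 12 months of follow-up (Protocol 3.1 and 4.5); 500 patients with at least 6 months each (4.3.1); sensitivity = TP / ACS events, with a Wilson interval and a null of 50% (4.4.1).

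**Assumptions.** True sensitivity s = 70%, with a range of 50% to 80%; the fraction of enrolled patients not evaluable, 0 to 40%; average follow-up at the analysis, 6 or 12 months; Poisson event counts with independent events. The sponsor's own sensitivity, power and event-rate inputs are redacted.

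**The plan's own figure.** For this reason 41 and 5,228 cannot be reproduced, only checked for plausibility. With 41 events the Wilson rule needs at least 27 detected (26 gives a lower bound of 48.1%, 27 gives 50.5%). Exact power is 77.6% at a sensitivity of 70% and 81.7% at 71%. The target is sensible.

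**Step 1: implied event rate.** 41 / 5,228 = 0.00784 per enrolled patient-year.

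**Step 2: expected ACS events, m.** The minimum follow-up is 500 × 0.5 = 250 patient-years, so m = 250 × 0.00784 = 1.96. If a fraction L of enrolled patients is not evaluable, divide by (1 − L).

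**Step 3: chance that the bootstrap interval fails.** It is undefined with no event, and has zero width when all events agree. Given k events, the chance that all agree is s^k + (1 − s)^k for k of 2 or more, and 1 for k = 1. Summing over Poisson counts gives

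P = e^(−m(1−s)) + e^(−ms) − e^(−m).

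At m = 1.96 and s = 0.7: 0.555 + 0.254 − 0.141 = 0.668.

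| Average follow-up | L | m | P at s = 0.7 |
|---|---|---|---|
| 6 months | 0 | 1.96 | 67% |
| 6 months | 20% | 2.45 | 57% |
| 6 months | 35% | 3.02 | 48% |
| 6 months | 40% | 3.27 | 44% |
| 12 months | 0 | 3.92 | 35% |
| 12 months | 40% | 6.54 | 15% |

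For s from 50% to 80%, P is 61% to 74% at m = 1.96, 26% to 48% at 3.92, and 7% to 27% at 6.54. At m = 1.96 the chance of no event is 14%, and of no more than one event 42%.

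**Step 4: what would be printed** (one event per patient).

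- Resamples with no ACS event: (1 − 2/500)^500 = 13.5% with two event patients, about 135 of 1,000; (1 − 3/500)^500 = 4.9% with three. Each gives 0/0.
- 2 of 2 detected: the bootstrap SE is 0 and the interval is 100% to 100%. The Wilson lower limit is 2 / (2 + 1.96²) = 34%. The exact lower limit is √0.025 = 16%.
- 1 of 2, 1 of 3 or 2 of 3 detected: the simulated percentile interval is 0% to 100%.
- GEE: a trial fit to 2 of 2 and 3 of 3 detected gave intercepts of about 22 on the logit scale with separation warnings, and 0 of 2 gave about −22. There is no finite estimate. With mixed outcomes a fit exists, but a robust variance from two or three clusters is unreliable.

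**The case against.** The strongest case on the other side has four parts.

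1. **Nothing is decided here.** The estimate is labelled preliminary, the GEE and bootstrap are additional analyses, and the readable text ties no hypothesis, stopping rule or go/no-go to them. This stands, and it limits the severity.
2. **The counts are already required.** A reader would see TP and FN beside the estimate, and the DSMB must include a statistician. This stands too. What is missing is a valid interval.
3. **250 patient-years is a floor.** Section 4.3.1 censors complication-free patients at the analysis date, and nothing readable limits sensitivity events to the first 6 months. This also stands. At 6.54 expected events the failure chance falls to 15%, but at 3.92 it is still 35%.
4. **A GEE that fails to converge is visible**, and a statistician would report it as not estimable. This is fair. Zero width describes the bootstrap, and the GEE's fault is a different one.

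A reader might infer that the plan's figures themselves imply three events. They do not: they give 1.96, and reaching 3 needs about 35% of enrolled patients not evaluable, which the readable text does not state. In the other direction, the cut-off counts clinical events, so if some of the 41 are Non Events the ACS count would be lower still.

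**Conclusion.** The point holds as a minor one. In the minimum follow-up the plan's figures imply about 2 ACS events. At an assumed sensitivity of 70%, the bootstrap interval is then undefined or zero-width about two times in three. The chance falls to 44% at 3.3 expected events, 35% at 3.9 and 15% at 6.5, and those counts rest on assumed attrition or longer follow-up. When it is not degenerate with two or three event patients, the percentile interval spans 0% to 100%, so it informs in neither case. The GEE has no finite estimate when all events agree, and too few clusters otherwise.

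A reader might go further and infer that the efficacy conclusion or the continuation of the study is at risk. The documents do not support that. The final test uses a Wilson interval, which does not collapse, and no readable rule acts on the preliminary sensitivity.

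**What to change.** In 4.3.1, replace the GEE and the bootstrap for sensitivity with a Wilson interval on TP out of ACS events, using the counts already required. Wilson is the plan's own method in 4.4.1; an exact interval would also serve. Show subgroup sensitivity in this phase as counts only.

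Move the GEE sentence to the Additional Analysis of 4.4.1 rather than deleting it. In the readable text it appears only in 4.3.1, so deletion would remove the plan's only model that allows for several events per patient. About 41 events could support it there.

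The cost is a small change to SAP wording. The preliminary interval becomes wide, which is an honest picture of two or three events.

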4.3.2 Primary Safety Endpoint

The ST Monitoring Feature will be evaluated by the percentage of patients with false positive events. The percentage of patients with false positive events is calculated as the number of patients who experience false positives divided by the number of evaluable patients. A False Positive occurs when a clinical event does not occur within 72 hours following a Type I ST episode.

The hypothesis is formally expressed as follows:

H_0 : Percent of patients experiencing a false positive event in 12 months $\geq 15\%$

H_a : Percent of patients experiencing a false positive event in 12 months $< 15\%$

The desired outcome is to reject the null hypothesis at the 2.5% significance level. The null hypothesis will be rejected at the 2.5% significance level if the

Statistical Analysis Plan

upper bound of the 95% confidence interval for the percent of patients experiencing false positive events is less than 15%. The upper confidence bound will be calculated using the Wilson score interval method.

Patient Group

All enrolled patients who have a successful implant or system revision, complete the baseline follow up visit and have the ST Monitoring Feature and Patient Notifier turned ON will be included in the evaluation of this study endpoint. Data collection towards the study endpoint will begin after the Baseline visit.

Further, the analysis population for the primary safety endpoint will be those subjects with the Fortify[®] ST (upgraded), Fortify Assura[®] ST and Ellipse[®] ST. Data from subjects with a Fortify[®] ST device prior to being upgraded will not be included in this analysis.

Analysis

Primary Analysis

The primary analysis will be a complete case analysis where patients who are lost to follow-up before completing their 12 month visit without experiencing a false positive event will be considered non-evaluable and omitted from the analysis of the endpoint. Patients experiencing a false positive event and withdrawing before the 12 month visit will be included in the analysis. The proportion of patients experiencing false positives will be estimated by the number of patients experiencing a false positive event divided by the number of evaluable patients.

Imputation Analysis

A comparison of baseline characteristics of the subjects with missing data and those without missing data will be done to determine if there is evidence that the data are not missing at random (it is not possible to determine that data are missing at random). If the missing at random assumption is clearly violated by these comparisons, it is usually possible to find a sub-group that are not missing at random who have to be imputed differently, such as assigning the worst score to patients in the sub-group. If this resolves the missing at random difficulty, the sub groups will be given special scores and the remaining patients will be imputed as described above.

This analysis will use the patients from the complete case analysis to perform a logistic regression and an imputation procedure to impute false positive status for patients who were non-evaluable in the complete-case analysis. The imputations are described as follows: A logistic regression will be performed using the complete case patients, with the dependent variable dichotomous

Statistical Analysis Plan

false positive status and the independent variables for ischemic Cardiomyopathy and each of the four categories of non-ischemic Cardiomyopathies (Dilated, Hypertrophic, Restrictive and ARVD), age, gender, QRS duration > 120ms and EF% at the time of enrollment. The estimates of the coefficients and standard errors of the logistic regression will be used as the parameters of a multivariate normal distribution that will define the population of the logistic regression model parameters. Up to ten random samples logistic model parameters will be selected. For each random set of parameters, the non-evaluable patients will have their false positive status imputed as having experienced a false positive if their predicted logistic model response is >0.5, and not having experienced a false positive event otherwise. These imputed datasets will be created using PROC MI in SAS V9.2 or greater. An analysis of the hypothesis will be carried out for each complete imputed dataset, and the results will be combined across datasets to obtain one overall conclusion using PROC MIANALYZE in SAS V9.2 or greater.

Additional Analysis

[figure not shown]
An empirical analysis will be provided for the proportion of patients experiencing false positive events using the estimator described in the Primary Analysis section. The standard error of this empirical estimate will be calculated as the standard deviation of a bootstrap distribution. The bootstrap distribution will be constructed using 1,000 bootstrap resamples. Each bootstrap resample will be performed at the patient level, and each resample will have a total sample size equal to the total number of evaluable patients. A two-sided 95% bootstrap confidence interval will be provided.

Subgroup Analysis

The analysis of the primary safety endpoint will be performed on the following the subgroups of patients

- Coronary artery disease patients with cardiomyopathy
- Coronary artery disease patients without cardiomyopathy
- Patients with abnormal baseline ECGs, for each of six abnormal subgroup categories
- Patients with normal baseline ECGs
- Patients with arrhythmias
- Gender
- Patients alerted via Merlin.net and patients alerted via device Patient Notifier

Sample Size

optimize ST feature parameters. The analysis with a 3-month run-in period

[REDACTED]

[REDACTED]

[REDACTED]

